So, it is estimated that a sample of 53 patients in each study group (total 159 patients) would achieve a power of 80% (type II error, 0.2) to detect a statistically significant difference among the three groups as regards the fetal birth weight for a medium effect size (eta squared, η^2) of 0.25. The effect size (eta squared, η^2) is calculated as follows: $\eta^2 = \text{between-group sum of squares} / \text{total sum of squares}$. This calculation used a two-sided F test with a numerator degree of freedom ($k-1$) of 2, a denominator degree of freedom ($n-k$) of 156, and a confidence level of 95% (type I error, 0.05), where k is the number of groups and n is the total sample size. This sample size of 159 patients would achieve a power of 93% (type II error, 0.07) to detect a statistically significant difference among the three groups as regards the secondary outcome measures (IUGR, PTL, and NICU admission) for a medium effect size (w) of 0.3. The effect size (w) is calculated as follows: $w = \sqrt{(\chi^2/N)}$, where χ^2 is the chi-squared statistic and N

is the total sample size. This calculation used a two-sided chi-squared test with a confidence level of 95% (type I error, 0.05).

A medium effect size of $\eta^2 = 0.25$ or $w = 0.3$ for the primary or secondary outcome measures, respectively, has been chosen as it could be regarded as a clinically relevant difference to seek in this exploratory study.

Assuming an expected drop-out rate of approximately 10%, a total sample size of 180 patients (60 patients per group) will be recruited.

Statistical Methods:

Data will be collected, tabulated, then analyzed using IBM© SPSS© Statistics version 22 (IBM© Corp., Armonk, NY).

Normally distributed numerical data will be presented as mean and SD, and skewed data as median and interquartile range. Qualitative data will be presented as number and percentage. Comparison of normally distributed numerical data will be done using one-way analysis of variance (ANOVA). Skewed data will be compared using the Kruskal Wallis test. Categorical data will be compared using the chi-squared test, or Fisher's exact test when appropriate. A two-sided p-value <0.05 will be considered statistically significant.

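### The primary effect size is given as eta squared = 0.25, but 53 per group at 80% power reproduces only for Cohen's f = 0.25, which is eta squared of about 0.059

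*Combined protocol and SAP*

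**What the plan says.** All of this is in the Sample Size Justification of the combined protocol and SAP. The primary outcome is birth weight, compared across the three fasting groups, and the calculation is attributed to G*Power.

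- **Size and power.** The plan proposes "a sample of 53 patients in each study group (total 159 patients"), which "would achieve a power of 80% (type II error, 0.2") "for a medium effect size (eta squared, η^2) of 0.25".
- **Definition.** The sentence beginning "The effect size (eta squared, η^2) is calculated as follows" sets eta squared equal to the between-group sum of squares over the total sum of squares.
- **Test.** It is an F test with 2 and 156 degrees of freedom and "a confidence level of 95% (type I error, 0.05), where k is the number of groups".
- **Justification.** The section later repeats eta squared = 0.25 and says that it "has been chosen as it could be regarded as a clinically relevant difference to seek in this exploratory study".

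Cohen's f is not mentioned anywhere in the document.

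**The concern.** An eta squared of 0.25 means that fasting group explains a quarter of the variance in birth weight. That is a very large effect to need 159 women for only 80% power, which suggests that 0.25 was entered into the calculation on a different scale from the one the text describes.

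The effect size matters because it is the only basis given for the sample size. The plan says that usable prior data on these outcomes in fasting women are lacking, so it chooses an effect that could be clinically relevant. It gives no difference in grams and no SD. If the effect is mislabelled, readers are told that the study looks for 25% of variance explained when it is built to detect about 6%. They would then misjudge what a non-significant result rules out, and an observed eta squared near 0.06 would look trivial although it is the effect the study was powered for.

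**Working it through.** **Inputs, all from the Sample Size Justification:** k = 3 equal groups, 53 per group, N = 159, degrees of freedom 2 and 156, alpha 0.05, target power 80%, effect size 0.25.

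**Method.** Power of the one-way ANOVA F test comes from the noncentral F distribution with noncentrality λ = N·f², where f² = η²/(1 − η²).

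**Step 1: the plan's figures as written.**
- η² = 0.25 gives f = √(0.25/0.75) = 0.577 and λ = 159 × 0.3333 = 53.0.
- Power at N = 159 is above 99.99% (0.9999995), not 80%.
- The smallest group size reaching 80% is 11 (33 in total, power 81.3%). With 10 per group, power is 76.7%.
- Neither the sample size nor the power reproduces.

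**Step 2: other readings of 0.25, at alpha 0.05.**

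| 0.25 read as | f | η² | Power at N = 159 | Smallest n per group for 80% |
|---|---|---|---|---|
| η² (as written) | 0.577 | 0.25 | >99.99% | 11 |
| f² | 0.500 | 0.25/1.25 = 0.20 | 99.996% | 14 |
| η | 0.258 | 0.0625 | 83.1% | 50 |
| Cohen's f | 0.250 | 0.0625/1.0625 = 0.059 | 80.5% | **53** |

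Only Cohen's f returns both 53 and 80%. With 52 per group, power at f = 0.25 is 79.7%, so 53 is exactly the minimum.

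**Step 3: could another alpha or power target rescue η² = 0.25?** No. At 80% power, an alpha of 0.001 needs only 22 per group. At alpha 0.05, 99% power needs only 23.

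**Step 4: size of the discrepancy.**
- Variance explained: 0.25/0.0588 = 4.25 times too large.
- Solving for exactly 80% power at N = 159 gives f = 0.2485 and η² = 0.0582, a ratio of 4.30.
- With three equally spaced means, the gap between the extreme groups is f·√6. That is 0.25 × 2.449 = 0.61 SD for the effect actually used, against 0.577 × 2.449 = 1.41 SD for the effect stated.
- If instead one group differs from two equal groups, the gap is 3f/√2: 0.53 SD against 1.22 SD.
- In grams, for equally spaced means and an assumed SD of 400 to 500 g (not in the plan), the gap is about 245 to 306 g against 566 to 707 g.

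**Step 5: is the problem wider?** No. The secondary calculation (chi-squared, w = 0.3, N = 159, 2 degrees of freedom) gives 93.3%, which agrees with the plan's 93%.

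**The case against.** The arithmetic cannot be rebutted, but several points can be made about how much it matters.

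- **No design element changes.** The sample size, groups, test and significance level are all unaffected. For the effect literally stated, the study has more power than claimed, not less. This is true, and it is why the fix costs no patients. It does not make the power statement for the primary outcome correct.
- **The analysis does not use the planning effect size.** The F test, its p-value and the observed group differences do not depend on it, and no decision rule compares results with eta squared = 0.25. This also stands. The harm is confined to how readers judge what a null result excludes and how they weigh an observed effect; the validity of a significant result is not in doubt.
- **The study is exploratory and its relevance claim is hedged.** Even so, the plan names a primary outcome, an alpha and a power, and the effect size is its sole justification for N.
- **The word medium may show that f was meant.** It is compatible with the diagnosis. But the symbol, the sum-of-squares formula and the later restatement all agree with one another, so a reader could not infer f from the text.
- **The gram figures rest on an SD and a pattern of means that the plan does not give.** Agreed. They illustrate the scale, and the conclusion does not depend on them.

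**Conclusion.** The concern holds. Under the plan's own definition, eta squared = 0.25 is inconsistent with 53 per group and 80% power: the power would exceed 99.99%, and 11 per group would suffice. The calculation matches Cohen's f = 0.25, eta squared = 0.059, so the variance explained by the target effect is overstated 4.25-fold. The finding assumes only what the plan states: three equal groups, a one-way ANOVA F test and alpha 0.05. That the authors intended f is an inference, though a strong one, since it is the only reading tried that recovers both figures. The sample size is correct for f = 0.25. The primary sample-size statement is wrong as written and must be corrected, because the clinical-relevance claim is attached to an effect the calculation did not use.

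**What to change.** In the Sample Size Justification:

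1. Replace eta squared of 0.25 with Cohen's f = 0.25 (eta squared = 0.059) in both places, the power statement and the later paragraph on clinical relevance.
2. Keep the sum-of-squares ratio only as the definition of eta squared, and define the effect size used as f = √(η²/(1 − η²)).
3. Have the investigators confirm that about 6% of birth-weight variance is an effect they regard as clinically relevant. Relabelling alone does not establish this.
4. State the corresponding difference between group means in grams, with the assumed SD, its source and the assumed pattern of means.

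Items 1 and 2 are wording changes. Items 3 and 4 need a short clinical judgement and a choice of SD. N = 159, the recruitment target of 180 and the secondary power statement stay as they are; no further patients are needed.

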Concurrence of fasting with pregnancy as a physiological condition introduces some controversies regarding the condition of the mother and the fetus. Pregnant women are exempt from fasting if it poses a risk to the fetus; however, many still fast while others are more cautious about its practice. Many pregnant show great interest in fasting and are able to perform this religious practice; however, they are concerned about their fetus and inquire about the possible associated complications during pregnancy According to the statics, in West Africa, 90% of pregnant women fasted during the month of Ramadan. The prolonged hunger presents itself as hypoglycemia or hyperketonuria, which may affect the neonatal weight, neonatal mortality and disability. During fasting, pregnant and breastfeeding women experience changes in metabolism, sleep patterns and daily physical activity (*Cuningham et al., 2010*).

Most Muslims observe Ramadan every year. Exemption from fasting is permitted for women who are pregnant or breastfeeding, but the missed fasts must be completed before the next Ramadan (**Rashed, 2010**).

Muslim women choose to fast during pregnancy because of a sense of religious duty, familial support, positive views on fasting, and difficulty in completing the missed fasts at another time. A previous study found that Muslim women believed the only reason not to fast would be perceived harm to mother or fetus, but that fasting during pregnancy is safe for healthy women. Women feel strong spiritual, emotional, physical, and social benefits from fasting; it is seen as a way of maintaining cultural identity and unity among their communities (**Robinson et al., 2005**).

Many women asking their obstetrician if fasting is safe for their baby or not? There have been many studies on metabolic changes and different aspects of human health during and after Ramadan, but there have been few studies on the effect of fasting on pregnancy outcome and there are also some controversies in the findings of different studies (**Ziaee et al., 2006**).

Ramadan fasting during pregnancy is a controversial issue. A group of pregnant women do not fast due to the probable harmful effect on fetal health. Although Ramadan fasting may be postponed to the postnatal period, some pregnant women obey it as a religious activity (*Joosoph, 2004*).

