There are several reports regarding the effects of Ramadan fasting on the human metabolism. Fasting leads to a decrease in serum glucose, insulin, lactate, and carnitine, as well as an increase in free fatty acids, hydroxy butirate, cholesterol, and triglyceride levels. As we know, maternal glucose infusion causes stimulation of short-term fetal activity and uteroplacental blood flow is essential for fetal development and wellbeing (*Osol, 2009*).

During the month of Ramadan, healthy adults abstain from food and drink from dawn to sunset. Pregnant are allowed, if they choose, to postpone the fast until after delivery. However, most of the women would like to fast with their families rather than doing this alone later. Therefore, most Muslim pregnant women fast during the holy month of Ramadan. Consequently, diet restriction and fasting could adversely affect pregnancy outcome, especially if Ramadan

*The Effect of 3rd trimester Ramadan fasting on Obstetric outcome
(Study Protocol)*

falls during the hot summer months with long days of fasting
(Mirghani, 2006).

Aim of the Work

This study aimed to find out the association between fasting during Ramadan and obstetric outcome in third trimester regarding to hypoglycemic symptoms, fetal growth, AFI, mode of delivery, birth weight and neonatal outcome.

Study question:

In pregnant women in the third trimester, does fasting during the holy month of Ramadan has a poor obstetric outcome regarding to hypoglycemic symptoms, fetal growth, AFI, mode of delivery, birth weight and neonatal outcome?

Patient and Methods

Type of the study :

Prospective Comparative Cohort Study.

Study setting :

EL- Demerdash outpatient clinic.

Duration of the setting :

The Holy month of Ramadan (from 18th June To 16th July 2015. Avenge hours of fasting 16 hours.

Population (study will include):

The patients will be recruited from outpatient clinic during Ramadan then followed during the holy month then grouped into three groups A ,B, C regarding fasting state and each group contain 53 patient after exclusion drop out patient

A- Non fasting group

B- Partially fasting group (average days of fasting 10-20 day).

C- Totally fasting group

Inclusion criteria:

- *Within the range of 20 – 35 years.*
- *3rd trimester pregnancy (starting from 28 weeks) which is going to be calculated according to the date of the last menstrual period & confirmed by ultrasonography.*

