- *Normal healthy women with average body mass index (BMI). Normal range (18.5 to 25).*
- *Women included have no medical disorder.*

Exclusion criteria :

- *History of systemic disorder.*
- *Smoking narcotics or alcohol use.*
- *Have previous history of fetal loss.*
- *Multiple pregnancies.*

Methodology

Women who fulfilled the eligibility criteria are going to be subjected to:

1) Complete history taking:

- a. Personal history.*
- b. Medical history.*
- c. Obstetric history.*
- d. History of present pregnancy: with special emphasis on signs & symptoms of hypoglycemia in the form of fatigue, dizziness, fainting, blurred vision, vomiting.*
- e. Fetal kicks.*

2) General examination: assessment of vital data.

3) Ultrasound fetal biometry every 2 weeks till delivery looking for

- **Fetal biometry.**
- **AFI (ammonic fluid index)**
- **Doppler.**

4) Fetal weight after delivery.

Sample Size Justification:

*The required sample size has been calculated using the G*Power Software (Universität Düsseldorf, Germany).*

The primary outcome measure is the difference between the three study groups as regards the fetal birth weight. The secondary outcome measures are the incidence of unwanted fetal outcomes (e.g., IUGR, PTL, or NICU admission).

Since there is currently no adequate information regarding the outcome measures in patients who are fasted for the whole or part of the month, the current exploratory study would target an effect size that could be clinically relevant.

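### Fasting groups are self-selected but every planned comparison is unadjusted, so a birth-weight difference, or its absence, cannot be separated from measurable group differences such as gestation and parity

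*Combined protocol and SAP*

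**What the plan says.** The design is a prospective comparative cohort with no randomisation. Under Population, women are "recruited from outpatient clinic during Ramadan then followed during the holy month then grouped into three groups" according to how much they fasted. The introduction links that choice to the outcome: "A group of pregnant women do not fast due to the probable harmful effect on fetal health". The Study question asks "does fasting during the holy month of Ramadan has a poor obstetric outcome", and Sample Size Justification makes birth weight the primary outcome.

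Statistical Methods gives the whole analysis. For numerical data that are normally distributed, "Comparison of normally distributed numerical data will be done using one-way analysis of variance (ANOVA"); skewed data go to Kruskal-Wallis, and categorical data to chi-squared or Fisher's exact test. The sample-size F test has 2 and 156 degrees of freedom, so no covariate is allowed for. Regression, matching and stratification are not mentioned anywhere.

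The data relevant to adjustment are these:

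- Gestation at entry is open-ended: "3rd trimester pregnancy (starting from 28 weeks) which is going to be calculated according to the date of the last menstrual period", with ultrasound confirmation.
- Parity is not named. It would be expected under "Obstetric history" in Methodology.
- BMI is restricted ("Normal healthy women with average body mass index (BMI). Normal range (18.5 to 25"), but the time of measurement is not given.
- Age is restricted to 20–35 years. Medical disorder, smoking, narcotics, alcohol, previous fetal loss and multiple pregnancy are excluded.

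**The concern.** When women form the groups by their own choice, nothing makes the groups comparable before fasting starts. If those who fast all month differ from those who do not in gestation or parity, and these factors are related to birth weight, the one-way ANOVA tests the fasting effect and the group differences together. The error can go either way: a significant result with no fasting effect, or a real effect hidden by an opposing imbalance.

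Timing adds to this. Recruitment runs during the month, "The Holy month of Ramadan (from 18th June To 16th July 2015", which is 28 days. Two women at the same gestation on enrolment can differ by up to 4 weeks in gestation when Ramadan began, so gestation at enrolment does not fix the stage of pregnancy at which exposure started.

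**Working it through.** **Inputs from the documents.** 53 per group, N = 159, three groups, two-sided alpha 0.05, effect size 0.25, stated power 80%.

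**Assumptions.** The documents give no birth-weight SD, no group imbalance and no strength of covariates. I take SD 400 or 500 g; a confounded gap b between the non-fasting group (A) and the totally fasting group (C), with the partially fasting group (B) midway; and covariates explaining R² = 0.05 to 0.2 of within-group variance.

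**1. The plan's own power.** Noncentrality is N·f² = 159 × 0.25² = 9.94. The critical value of F(2, 156) is 3.054, and power is 0.805. The stated 80% is reproduced when 0.25 is read as Cohen's f. The text labels it eta squared; read that way, power would exceed 99.9%. The masking figures in step 4 use f = 0.25 because it is the value that yields the stated power.

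**2. False positives with no fasting effect.** Means 0, b/2, b give f² = (b/SD)²/6, so the noncentrality is 159 × (b/SD)²/6. For b = 100 g and SD 400 g: 159 × 0.0625/6 = 1.656, and the rejection rate is 0.190.

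| Gap b | SD 400 g | SD 500 g |
|---|---|---|
| 25 g | 0.058 | 0.055 |
| 50 g | 0.082 | 0.070 |
| 100 g | 0.190 | 0.136 |
| 150 g | 0.384 | 0.258 |

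**3. The imbalance these gaps require.** A covariate difference of d SD between A and C shifts birth weight by d·√R² SD, so d = b/(SD·√R²). Over R² 0.05–0.2 and both SDs, 50 g needs 0.22–0.56 SD. At R² 0.1–0.2, gaps of 100–150 g need about 0.45–1.2 SD. Rejection rates by imbalance:

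| Imbalance d | R² 0.05 | R² 0.1 | R² 0.2 |
|---|---|---|---|
| 0.2 SD | 0.054 | 0.058 | 0.066 |
| 0.5 SD | 0.075 | 0.102 | 0.160 |
| 1.0 SD | 0.160 | 0.283 | 0.520 |

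**4. Masking, and what adjustment recovers.** With evenly spaced means, f = 0.25 is a C minus A difference of 0.25 × √6 = 0.612 SD (245 g at SD 400, 306 g at SD 500). An opposing gap leaves noncentrality 159 × (0.612 − b/SD)²/6.

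For the adjusted 2-df test with three covariates (denominator df 153), where the covariates carry the whole gap, the noncentrality is 9.94/[(1 − R²)(1 + d²/6)]. For R² 0.05 and d = 1.0: 9.94/(0.95 × 1.167) = 8.97, and power is 0.760.

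| Opposing gap | Unadjusted, SD 400 | Unadjusted, SD 500 | Adjusted, range over R² 0.05–0.2 and both SDs |
|---|---|---|---|
| 25 g | 0.709 | 0.730 | 0.820–0.887 |
| 50 g | 0.597 | 0.644 | 0.805–0.885 |
| 100 g | 0.361 | 0.453 | 0.745–0.877 |
| 150 g | 0.175 | 0.277 | 0.654–0.863 |

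**5. Type I error of the adjusted test.** Under this model it holds at 5%. Simulation with 40,000 replicates at R² 0.1 gave 0.048 at an imbalance of 0.5 SD and 0.051 at 1.19 SD.

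**The case against.** The strongest reply is that the documented reason for not fasting, concern for the fetus, is not what the proposed model adjusts for. No passage ties the choice to gestation or parity. This stands as a limit on the remedy: adjustment deals with measured factors only. It does not make the unadjusted comparison interpretable.

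Eligibility also removes part of the confounding, through age, BMI, health, substance use and previous fetal loss. That is true, but gestation beyond 28 weeks and parity stay open.

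The sizes are assumed, and weak covariates would matter little. At R² 0.02 the rejection rates for imbalances of 0.2, 0.5 and 1.0 SD are only 5.2%, 6.0% and 9.1%; at R² 0.01 they are 5.1%, 5.5% and 7.0%. The 38% and 52% figures are upper corners of the range, not expected values. Masking depends on reading 0.25 as f: at a literal eta squared of 0.25, power stays at or above 99.8% even against an opposing 150 g gap. The adjusted powers are best case, since they let the covariates carry the whole gap. All of this bears on the size of the problem, not on whether it exists.

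Finally, the aim is worded as an association and the study calls itself exploratory. The Study question nevertheless asks whether fasting leads to a poor outcome, and an unadjusted p-value would be read as the answer.

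**Conclusion.** The concern holds. Groups follow the women's own choice, every listed test is unadjusted, and the plan contains no other control beyond eligibility. I am confident of that much from the text. The direction and size of the bias cannot be derived from the documents. Under the assumptions above, the effect is small for slight imbalances (5.4–6.6% false positives at 0.2 SD) and serious for large ones (16–52% at 1.0 SD), with matching losses of power when the imbalance opposes a real effect. This should be fixed before analysis. The study is not invalid without the fix, but its primary result would be hard to interpret.

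**What to change.** - **Primary analysis.** Make it a linear model for birth weight on fasting group, adjusted for gestational age on 18 June 2015 (start of Ramadan, from the last menstrual period), parity and maternal age. Keep the 2-df group test as the single primary test at two-sided 0.05.
- **Supporting results.** Report adjusted C minus A and B minus A differences in grams with 95% confidence intervals, and keep the one-way ANOVA as the unadjusted supportive analysis.
- **Data.** State that parity is recorded and when BMI is measured. Add BMI to the model only if it is a pre-pregnancy or pre-fasting value.
- **What not to adjust for.** Leave out gestational age at delivery, which may lie on the causal path because preterm labour is a secondary outcome. Leave out first-scan fetal weight unless that scan preceded any fasting.
- **Secondary outcomes.** Adjust IUGR, preterm labour and NICU admission where event counts allow; otherwise label the comparisons as unadjusted.
- **Limitation.** State that confounding by perceived fetal risk remains.

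The cost is SAP wording, confirmation of two data items and a little more analysis. Power may change: about 89% with balanced covariates at R² 0.2; about 76% at 1.0 SD imbalance with R² 0.05, or 1.2 SD with R² 0.1; and about 65% in the most extreme case examined (1.68 SD at R² 0.05). The comparison is 80% for the unadjusted test with no confounding.
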